1.2 Quantitative Analysis Plan

The primary hypothesis is that receipt of YMHP (regardless of delivery format) will be associated with greater improvements in sexual health management (as measured by decreased STIs, CAS and increased PrEP uptake/adherence) as well as greater reductions in substance use, compared with youth who receive the standard of care (individual HIV testing) only. Our secondary hypothesis is that youth who elect to receive YMHP remotely will report more barriers to accessing health care compared to those who elect to receive the intervention in clinic. In addition, we hypothesize that remote-based YMHP will demonstrate greater improvements in sexual health management (as measured by decreased STIs, CAS, and increased PrEP uptake/adherence) as well as reductions in substance use, compared to clinic-based YMHP, among YMSM who do report barriers to health care access. In contrast, it is hypothesized that clinic-based YMHP will demonstrate greater improvements in sexual health management and reduced substance use among YMSM who do not report barriers to health care access. Self-management model analysis is described in the AC.

The AC will test the effect of clinic-based versus remote delivery on STI rates, alcohol and drug use behavior, CAS, and PrEP uptake through multi-level growth mixture modeling (GMM). A separate model will be run for each outcome. Each model will be a 2-level model in which individuals (Level I) are nested in clinics (Level II). This approach controls for the non-independence of individuals within clinics. Because three SRVs provide extremely limited predictive power at Level II, no site covariates are included in the model. (The models are empty at Level II).

In a GMM, a latent growth curve with an intercept and linear slope factor is specified. Latent class analysis is applied to these 2 growth components (intercept and slope) to identify groups of individuals who share trajectories. For example, with regard to drug or alcohol use, “immediate and sustained responders” may have the lowest post-intervention intercept and a flat slope. Meanwhile, “non-responders” might have the highest post-intervention intercept and a flat slope. In contrast, “delayed responders” might have a high post-intervention intercept but a significant negative slope, indicating reductions in missed medication over the follow up period.

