If modeling results indicate that discrete classes are not present, we will proceed with analyses in which the growth factors (intercept and slope) are predicted directly by intervention condition (and demographic factors found to be associated with condition after randomization or with attrition over follow up). GMMs can subsequently incorporate predictors of class membership. These analyses can be conceptualized as a multi-nominal logistic regression with the latent trajectory-class membership constituting the outcome. The predictors

of primary interest will be intervention condition, the presence of any barriers to health care access, and the interaction between condition and barriers to access. We will include as covariates any demographic variables that were associated with condition after randomization or with attrition over the follow up period.

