
1.2.2 Equivalency Checks

The AC will ensure that randomization is stratified by city and the presence of any barriers to healthcare access. Further, they will monitor randomization to ensure that condition is not associated with characteristics that would require adjustment in proposed analyses. To assess differential attrition, we will utilize a multilevel modeling approach (to account for the nesting of participants within clinic/city) to assess for condition, time, and condition \times time interaction effects in the proportion of completed assessments across the length of follow-up. Any evidence of differential attrition will be examined to determine whether there are baseline demographics, behavioral, or biological predictors that are associated with such differences in attrition. These effects will be adjusted for in subsequent analyses.

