1.2.3 Equivalency Tests

A series of bivariate analyses will be conducted to examine between condition differences at baseline and evaluate

the success of randomization procedures. We will utilize chi square tests of independence, t-tests, ANOVA and Spearman's rho correlations as appropriate to examine whether intervention conditions differed significantly with respect to key demographic variables and outcome variables at baseline. In the event that significant baseline differences are observed, these demographic factors will be incorporated into subsequent outcome analyses.

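### Neither outcome model prespecifies the baseline value of its outcome, so the no-classes growth model may give up some precision and a chance baseline imbalance has no assured correction

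*SAP*

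**What the plan says.** The primary hypothesis in SAP 1.2 is worded as change: "greater improvements in sexual health management (as measured by decreased STIs, CAS and increased PrEP uptake/adherence) as well as greater reductions in substance use". Two models are to test it, one set per outcome.

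- **Class-membership model.** The predictors are condition, barriers to health care access and their interaction. For the rest, the SAP says "We will include as covariates any demographic variables that were associated with condition after randomization or with attrition over the follow up period".
- **No-classes growth model**, used if discrete classes are not found. Each growth factor is to be "predicted directly by intervention condition (and demographic factors found to be associated with condition after randomization or with attrition over follow up"). Barriers to access are not named here.

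Three other statements bear on baseline outcomes.

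- SAP 1.2.3 tests whether "intervention conditions differed significantly with respect to key demographic variables and outcome variables at baseline". It continues: "In the event that significant baseline differences are observed, these demographic factors will be incorporated into subsequent outcome analyses".
- SAP 1.2.2 looks, where there is differential attrition, at "whether there are baseline demographics, behavioral, or biological predictors that are associated with such differences in attrition", and adjusts for what it finds.
- SAP 1.2.2 also has the analysis team "monitor randomization to ensure that condition is not associated with characteristics that would require adjustment in proposed analyses", and says that "randomization is stratified by city and the presence of any barriers to healthcare access".

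The SAP does not list the time points in the growth curve. Its worked example, about drug or alcohol use, places the intercept after the intervention. Protocol 9.0 lists a baseline and four follow-ups: the immediate post-test and 3, 6 and 9 months after it.

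**The concern.** Baseline condomless anal sex (CAS), heavy drinking days and drug use days are collected on everyone. At the standard visit they are collected before randomisation (Protocol 6.0, Randomization). They are likely to be among the best predictors of the same outcomes later. Leaving them out of a linear growth model has two costs: precision already paid for is not used, and a chance imbalance at baseline passes partly into the estimated effect.

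Choosing covariates by significance tests does not repair this. A covariate improves precision because it predicts the outcome, not because the arms happen to differ on it. The rule is written down, but the covariate set is not known until the tests have been run.

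**Working it through.** **Is there any assured route to adjustment?** Setting the SAP statements side by side:

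| Statement | Baseline outcome adjusted for? |
|---|---|
| 1.2, class-membership model | Not named |
| 1.2, no-classes model | Not named |
| 1.2.3, equivalency tests | Tested; as worded, only demographic factors are carried forward |
| 1.2.2, attrition | Only if differential attrition is found and baseline behaviour predicts it |
| 1.2.2, monitoring of randomisation | Could cover baseline outcomes, but states no adjustment |
| 1.2.2, stratification | City and barriers only |

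None of them ensures it.

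**Size, for the no-classes growth model.** The plan gives no figure of its own on this point, so the following is an illustration. It covers the three outcomes from the computerised survey: CAS, heavy drinking days and drug use days.

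*From the documents:* four follow-ups (Protocol 9.0); N = 270 (SAP 1.2.1, Protocol 2.0 and 12.0) or 180 (Protocol 1.0, and 60 at each of three sites in 25.0); rho .2 to .5 under compound symmetry (SAP 1.2.1, given there for STIs only).

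*Assumed:* the same rho range for these outcomes; baseline outside the curve; baseline correlating with each follow-up at b, with b = rho unless stated; linear approximation, unit variance, complete data; 1:1 allocation; two-sided alpha .05; everyone in YMHP versus standard of care, although before 10/15/19 the comparison was clinic versus remote.

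1. Code the follow-ups 0, 1, 2, 3. The least-squares intercept weights are .7, .4, .1, -.2 (sum 1, sum of squares .70). The slope weights are -.3, -.1, .1, .3 (sum 0).
2. Intercept variance v = rho + .70(1 - rho). Its covariance with baseline is b, so the adjusted variance is v - b². The slope's covariance with baseline is b × 0 = 0, so the slope gains nothing.
3. Power after adjustment, starting from .80, is Phi(2.802 × sqrt(v/(v - b²)) - 1.96).
4. With r = b/sqrt(v), and given a baseline z of 1.96, the unadjusted test statistic under the null is normal with mean 1.96r and variance 1 - r². The conditional false-positive rate is the probability that it lies beyond ±1.96.

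| rho | b | v | v - b² | Variance cut | Power | r | Error given baseline p = .05 |
|---|---|---|---|---|---|---|---|
| .2 | .2 | .76 | .72 | 5.3% | .82 | .229 | 6.7% |
| .5 | .5 | .85 | .60 | 29.4% | .92 | .542 | 14.3% |
| .5 | .3 | .85 | .76 | 10.6% | .84 | .325 | 8.4% |

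**The charitable reading of SAP 1.2.3.** Suppose the baseline outcome were added only when it differs at p < .05. Power would then be .802 (rho .2) or .813 (rho .5), so most of the gain is lost.

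**Size of the shift.** A baseline difference at exactly p = .05 is 1.96 × sqrt(2/135) = 0.24 SD at N = 270, or 1.96 × sqrt(2/90) = 0.29 SD at N = 180. Multiplied by b = .2 to .5, the unadjusted intercept effect moves by 0.05 to 0.12 SD or 0.06 to 0.15 SD. At N = 270 the effect detectable with 80% power is 2.802 × sqrt(v) × sqrt(2/135) = 0.30 to 0.31 SD, so the shift is 16% to 38% of it. That ratio and the error rates do not depend on N.

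**Overall error.** Averaged over all randomisations, the unadjusted rate is 5%. A baseline difference at p < .05 has a 5% chance for each outcome.

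**The case against.** The strongest reply concerns scope and size, and much of it stands.

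- **Which model.** The class-membership model is the lead analysis, and the arithmetic does not carry over to it. In a multinomial logistic model a prognostic covariate also changes the coefficient being estimated. A reader might infer that every primary analysis loses precision; the documents do not support that.
- **Strength of the correlation.** Entry requires recent substance use and either CAS or a positive STI test (Protocol 10.0). That may narrow the baseline range and weaken its correlation with follow-up. The b = .3 row shows the effect: a cut of about 11%, not 29%. At rho .2 the gain is small in any case.
- **Conditional error.** A reader might take 7% to 14% as the trial's false-positive rate. It is not: it applies only given a baseline difference at p = .05.
- **Time points.** Baseline may have been meant as a point on the curve. The only hint against this is an example about drug or alcohol use, which also mentions missed medication and may be carried-over text. For CAS there is no direct evidence either way.
- **STIs and PrEP.** STI testing is scheduled at only two follow-ups, and a reader might extend the point to that model. But Protocol 6.0 also provides mailed kits and make-up tests, and the choice of STI model is a separate issue. For PrEP uptake, current Truvada users are excluded, so baseline has little to offer.

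What the reply does not supply is a statement that ensures adjustment for a baseline outcome. The uncertainty about time points is itself something the SAP should settle.

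**Conclusion.** The point holds within limits. Neither outcome model prespecifies the baseline value of its outcome, and no other part of the SAP guarantees that it will enter. If the curve uses post-intervention points only, the cost in the no-classes model is small to moderate: about 5% to 29% of intercept variance, nearer 11% if baseline correlates at .3 with follow-ups whose own correlation is .5, and nothing on the slope. These figures rest on a correlation range that the SAP gives only for STIs.

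The trial's overall type I error is not affected. What is missing is protection in the particular trial where CAS, heavy drinking days or drug use days happen to differ between arms at baseline. This should be put right because the data already exist and the change is cheap; it does not invalidate the analysis.

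**What to change.** Revise SAP 1.2, 1.2.2 and 1.2.3 as follows.

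1. State which time points enter the growth curve for each outcome.
2. Where baseline is not a modelled point, prespecify the baseline value of CAS, heavy drinking days or drug use days as a covariate on the growth factors and in the class-membership model. Use values collected before randomisation.
3. Say how remote baselines completed after randomisation are handled. For virtual visits, Protocol 6.0 places randomisation after HIV testing and before the intervention, and does not clearly place all other baseline data before it.
4. Where baseline is a modelled point, constrain baseline means to be equal across arms instead.
5. Add the barriers stratum to the no-classes model.
6. Replace selection by baseline significance tests with this fixed set, and keep the baseline comparisons descriptive. Baseline predictors of attrition may stay, to support the missing-at-random assumption in SAP 1.1.

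No new data are needed. The no-classes model gains up to four parameters per outcome (baseline outcome and barriers, each on intercept and slope). A class model with K classes gains K - 1 for the baseline outcome. Keeping participants with no baseline value under full-information maximum likelihood adds the parameters of the baseline distribution, such as a mean and a variance.

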1.2.1 Power Analysis

First, we analyzed power assuming independence of participant observations (assuming that the nesting of people-within-clinic was irrelevant). With regard to STIs, we utilized the “repeated measures” module of PASS 13.0 to examine power to detect odds ratio differences in a repeated measures design. Specifying compound symmetry, we allowed ρ to vary between .2 and .5. Assuming the prevalence of STIs in the remote-based condition varies between .05 and .15, the proposed design ($N = 270$) has power .80 to detect an odds ratio of .20 to .50. Similarly, with regard to the odds of PrEP uptake, allowing the rate of uptake in the remote-based condition to vary between .05 and .20 and allowing ρ to vary between .4 and .7, the proposed design has power of .80 to detect an odds ratio of 1.9 to 2.3. With regard to number of alcohol and drug use days, we utilized the *Tests for Two Poisson Means* module in PASS 13.0. Based data from our previous studies, we allowed the rate of heavy drinking in the phone-based condition to vary between 7 and 9 days during a 30-day assessment. The study is adequately powered to detect a 3% reduction in number of heavy drinking days in the clinic-based condition at any single follow up point. Allowing the rate of drug use in the remote-based condition to vary between 3 and 5 days during a 30 day assessment period, the study is adequately powered to detect a 4% reduction in drug use in the clinic-based condition. A similar analysis was conducted with respect to CAS. Based on our previous research, we allowed the rate of CAS in the phone-based condition to vary between 2 and 4 acts in a 30 day assessment period. The study is powered to detect a difference as small as 5% between the remote and clinic-based YMHP conditions. The nesting of individuals within SRVs has the potential to reduce power because substantial variability in outcome across SRVs can obscure level II treatment effects [70, 71]. The design effect can be used to tailor power analyses calculated under assumptions of independence. In the case of a Level I predictor with a fixed effect which is uncorrelated with other covariates in the model, the design effect is equal to the $1 - \rho$, where ρ is the intra-class correlation or the percentage of variance accounted for by variability between SRVs [71]. In previous intervention trials conducted within the ATN [72], between clinic site variability in HIV related outcomes did not differ significantly from zero. Based on the characteristics of ATN clinics, we anticipate a similar absence of variability across clinics, suggesting that the design effect would result in a negligible reduction in power. Finally, a sample size of 270 is sufficient to detect a moderation effect with an f^2 of .02. Cohen [73] designates this as a small effect, however recent work has characterized an effect of this size as moderate to large as applied to moderation [74].

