## **12.0 Local Number of Subjects**

Anticipated enrollment: 270 YMSM

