1.0 DATA MANAGEMENT AND ANALYSIS PLAN

1.1 Data Management and Data Quality

The SIU MC will be handling data management for the randomized controlled trials in a standard manner including scale scores, composites, syntax, etc. in order to facilitate rapid analyses by the AC. Data will be entered directly by participants through Qualtrics using systems established by the REC. Data dictated by participants who request assistance completing surveys may also be entered by the site RA. The database, data structure, and data quality will be routinely reviewed by the REC with support from the AC. Where indicated, we will use full-information maximum likelihood estimation to account for missing data under missing at random assumptions.

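### The power of .80 stated for STIs and PrEP in SAP 1.2.1 rests on the full enrolment target of 270, with no allowance for the loss that the plan expects

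*SAP*

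**What the plan says.** For STIs, SAP 1.2.1 states that "the proposed design ($N = 270$) has power .80 to detect an odds ratio of .20 to .50". For PrEP uptake it states that "the proposed design has power of .80 to detect an odds ratio of 1.9 to 2.3"; no number is repeated there, and 270 is implied. For moderation it says "a sample size of 270 is sufficient to detect a moderation effect with an f^2 of .02", with no power level. The alcohol, drug-use and CAS claims refer only to the study and give neither a sample size nor a power level. The heavy-drinking claim, for example, reads: "adequately powered to detect a 3% reduction in number of heavy drinking days in the clinic-based condition at any single follow up point".

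Protocol 12.0 gives "Anticipated enrollment: 270 YMSM", and Protocol 2.0 splits this into 90 at each of three sites. The number in the power analysis is therefore the number to be enrolled. The only adjustment that SAP 1.2.1 discusses is the design effect for clinics, which it judges negligible.

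The plan provides for loss in several places:
- SAP 1.1: where indicated, "we will use full-information maximum likelihood estimation to account for missing data under missing at random assumptions".
- SAP 1.2: covariates associated with attrition enter the models.
- SAP 1.2.2: condition, time and their interaction are examined "in the proportion of completed assessments across the length of follow-up".
- Protocol 14.0: there are rules for withdrawal, death and administrative removal after randomisation. Some people counted as enrolled are not randomised (those who withdraw after baseline but before randomisation, or are found ineligible during baseline).
- Protocol 6.0, COVID-19 modifications: at the 3- and 9-month visits, which normally require biological testing, only the survey is completed.

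Neither document gives a retention rate.

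**The concern.** A detectable odds ratio solved for power .80 at a given number has no slack. If that number is everyone enrolled, the .80 holds only when every enrolee is randomised and supplies every outcome used. The plan does not expect this. Maximum likelihood under missing at random uses the observed visits and limits bias, but it does not restore the information in visits that did not happen.

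What is at stake is how the STI and PrEP results are read. A reader who takes .80 at face value would give a null result more weight than the data analysed can support. No estimate or test is affected; the planning statement is.

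**Working it through.** **Inputs.** From SAP 1.2.1: N = 270; STI prevalence .05 to .15 in the reference condition; within-person correlation ρ from .2 to .5 with compound symmetry; stated power .80 for odds ratios .20 to .50. From Protocol 6.0: STI tests at baseline and at the 3- and 9-month follow-ups, so two after baseline. Not stated, and assumed here: two-sided alpha .05, 1:1 allocation, the number of measures M, all loss rates, and that the lower odds ratio goes with the lower prevalence.

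**1. Reproducing the STI figure at 270 with no loss.** The effective number per arm is 135 × M / [1 + (M − 1)ρ], entered in a two-proportion test. An odds ratio of .20 takes .05 to .0104; an odds ratio of .50 takes .15 to .0811.

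| M | ρ | Effective n per arm | Power, OR .20 from .05 | Power, OR .50 from .15 |
|---|---|---|---|---|
| 2 | .2 | 225 | .690 | .629 |
| 2 | .5 | 180 | .593 | .534 |
| 3 | .2 | 289.3 | .796 | .738 |
| 3 | .5 | 202.5 | .644 | .583 |
| 4 | .2 | 337.5 | .853 | .801 |
| 4 | .5 | 216 | .672 | .611 |

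Other variants were tried: M from 1 to 5, one-sided .05, and 2:1 and 1:2 allocation. No single setting gave .80 at both ends. Because M, alpha and allocation are unstated, the result is that the figure could not be reproduced, not that it is proved wrong. Nothing in these results suggests a built-in dropout margin: with M = 4 and ρ = .2, an odds ratio of .50 needs a total of exactly 270 before any loss.

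The PrEP figure was not reproduced either. With M = 4, and ρ = .4 and .7 in turn, power at 270 is .664 and .519 for an odds ratio of 2.3 from .05, and .871 and .739 for 1.9 from .20.

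**2. Effect of loss if .80 at 270 is taken as correct.** At power .80 the standardised effect is 1.960 + 0.842 = 2.802. With a fraction R of the information retained, power = Φ(2.802√R − 1.960).

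| Complete loss (assumed) | Number with data | 2.802√R − 1.960 | Power |
|---|---|---|---|
| 10% | 243 | 0.698 | .757 |
| 15% | 229.5 | 0.623 | .733 |
| 20% | 216 | 0.546 | .707 |
| 30% | 189 | 0.384 | .650 |

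**3. Crediting partial follow-up.** With two STI tests under compound symmetry, a person with both contributes 2/(1 + ρ), a person with one contributes 1, and a person with none contributes 0. If shares b and s give both tests and one test, R = b + s(1 + ρ)/2.
- 80% both, 10% one, 10% none: R = .80 + .10 × .60 = .86 (ρ = .2) or .80 + .10 × .75 = .875 (ρ = .5). Power is .738 or .746.
- 70% both, 15% one, 15% none: R = .79 or .8125. Power is .702 or .714.

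**4. Detectable effect.** With M = 3 and ρ = .2, a 20% loss moves the odds ratio detectable at .80 from .197 to .131 (prevalence .05) and from .468 to .419 (prevalence .15).

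**5. Moderation.** With one degree of freedom and noncentrality f² × N = .02 × 270 = 5.4, power is .64. At 216 it is 4.32 and power is .54. A power of .80 would need 395.

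**6. Count outcomes.** A two-Poisson-means test depends on the exposure entered, which is not stated. With exposure 30, power over the stated ranges is .88 to .995 at 270 and .80 to .98 at 216. At 189 the lowest drug-use and CAS cases fall to .75 and .77. With exposure 1, power is only about .08 to .13 at 270, before any loss.

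**The case against.** The case against the point has four parts.

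*Scope.* A reader might infer that every power figure uses all 270 and that each promises .80. The text does not support this. The number 270 is explicit only for STIs and moderation, and .80 is explicit only for STIs and PrEP. A reader might also take the phrase "in the clinic-based condition at any single follow up point" to mean that the count claims fall with every missed visit. Step 6 does not bear that out: they either keep at least .80 after a 20% loss or fail before any loss. This objection stands and narrows the point to STIs and PrEP, with moderation in principle.

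*Magnitude.* The loss rates are assumptions, and the starting .80 could not be reproduced. It would be wrong to say as fact that the trial detects its target effects 65% to 75% of the time. This also stands. The figures in steps 2 and 3 are conditional.

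*Mitigation.* Protocol 6.0 asks for missed 3- or 9-month tests at the next assessment, offers mailed kits and allows surveys by link. These reduce loss but do not remove it. The COVID-19 section has some participants complete only the survey at visits that would normally include testing. That affects the STI outcome directly; it does not by itself remove survey data.

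*Priority.* Protocol 1.0 gives 180, and Protocol 25.0 gives 60 per site. Taken alone, 180 would give Φ(2.802 × √(180/270) − 1.960) = .63, a larger fall than a 30% loss. The power analysis also compares clinic with remote delivery, whereas the primary hypothesis and the randomisation compare YMHP with HIV testing. Both are true. They are reasons to redo the calculation once with retention included, not reasons to leave retention out.

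**Conclusion.** The point holds for STIs and PrEP. SAP 1.2.1 sets its number equal to planned enrolment and allows nothing for loss, while the plan itself provides for attrition and missing data. Any net loss of STI or PrEP data puts power below the stated .80 at the stated odds ratios.

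The size is conditional on .80 at 270 being right, two-sided alpha .05 and assumed loss. Power would be about .76, .71 and .65 at 10%, 20% and 30% complete loss, and .74 to .75 in the 80/10/10 case.

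The moderation claim is exposed in principle, though it names no power level. The count-outcome claims are not shown to change. Nor do the documents support reading attrition as the only reason that .80 may fail, since in most settings tried the STI figure falls short at 270 with complete data.

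**What to change.** In SAP 1.2.1:
- Restate STI and PrEP power, or the detectable odds ratios, and the moderation figure at the expected number with data at each analysed visit. Use observed retention pooled over arms (Protocol 14.0 already defines who stays in the retention denominators), or show 10%, 20% and 30% loss side by side.
- State alpha and sidedness, the number of repeated measures and the allocation ratio, so that the figures can be reproduced.
- Do this for the randomised comparison of YMHP with HIV testing.
- First reconcile the enrolment figure: 270 in Protocol 2.0, Protocol 12.0 and SAP 1.2.1, against 180 in Protocol 1.0 and 60 per site in Protocol 25.0.

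The cost is SAP wording and one re-run calculation. It adds no participants and needs no data by arm. The stated power or detectable effects become less favourable.

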### **Randomization**

Participants will be randomized after completing the baseline assessment (i.e., CASI and specimen collection), but prior to their first YMHP session. Participants are randomized into one of two intervention conditions: 1) YMHP (delivery of the YMHP intervention in person or

**PROTOCOL TITLE:** Comparative effectiveness trial of clinic-based delivery of an HIV risk reduction intervention (YMHP) for YMSM, Phase 2

remotely), or 2) a standard of care HIV Testing and counseling session with referrals to other available services. . If the participant is randomized to YMHP, the first YMHP session will always be conducted in person after the baseline assessment. In the event a participant does not wish to complete the first YMHP session immediately after the baseline assessment, the SRV will postpone the participant's randomization. Randomization will then occur when the participant returns to the SRV for their first YMHP session. If the participant is randomized to HIV Testing, no additional intervention procedures are required, because HIV testing is conducted in conjunction with the Baseline appointment. However, the CHW will meet with the participant to ensure that any individual risk assessment is administered and referrals for PREP and other prevention services are given consistent with clinic standards of care for individual HIV testing.

**COVID accommodations-** In the event the baseline visit is conducted virtually (see below for details), randomization will still occur after HIV Testing and before the intervention. Since many individuals who are randomized to HIV testing only will have already received that portion of the appointment, randomization may occur before scheduling session 1.

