1. CASI (\$25)
2. 2. Optional Qualitative Feedback Interview (\$25)

*Follow-up Assessments*

There will be four additional follow up assessments for participants to complete. These follow up assessments will occur in 3-month intervals until 12 months after their IP (i.e., 3 months, 6 months, 9 months after the IP).

The 3-month and 9-month follow-up assessments include completing a CASI and require a

**PROTOCOL TITLE:** Comparative effectiveness trial of clinic-based delivery of an HIV risk reduction intervention (YMHP) for YMSM, Phase 2

confidential urine drug test, HIV and STI testing. The urine drug test, HIV and STI testing should be performed at the SRV, or by using a self-test kit which will be mailed to the participant if they choose. If participants do not complete the 3 month or 9 month urine drug test, HIV and STI testing they will be asked to complete these tests at their next assessment.

The 6-month assessment does not require urine drug test, HIV and STI testing so therefore these assessments can be completed using an electronic link we send to participants or they can complete the CASI at the ATN site if they choose. This survey will be similar to the baseline survey and it will take about 45 minutes to complete.

*3-month follow-up & 9-month follow-up (up to \$50)*

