## 9.0 Study Timelines

Individual participants are in the study for twelve months (Baseline, Immediate post-test assessment, 3-month follow-up, 6-month follow-up, 9-month follow-up,)

All study subjects will be enrolled over the course of 48 months.

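### The stated PrEP power (odds ratio 1.9 to 2.3 at 80%) is not reproduced at the 5% uptake that the SAP itself assumes

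*SAP*

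**What the plan says.** SAP 1.2.1 (Power Analysis) first treats STIs with a repeated-measures module: "Specifying compound symmetry, we allowed ρ to vary between .2 and .5", and "the proposed design ($N = 270$) has power .80 to detect an odds ratio of .20 to .50". It then carries the approach to PrEP uptake. The reference rate is given a range: "allowing the rate of uptake in the remote-based condition to vary between .05 and .20". The within-person correlation is given a different range from the one used for STIs: "allowing ρ to vary between .4 and .7". The section concludes from these inputs that "the proposed design has power of .80 to detect an odds ratio of 1.9 to 2.3".

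For this calculation the section gives no alpha, sidedness, allocation ratio, number of repeated measures, attrition allowance or form of contrast.

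The protocol supplies some of these:
- Two arms (6.0, Randomization): "Participants are randomized into one of two intervention conditions". These are YMHP and standard-of-care HIV testing. No ratio is given.
- Four post-baseline assessments (9.0): "Individual participants are in the study for twelve months (Baseline, Immediate post-test assessment, 3-month follow-up, 6-month follow-up, 9-month follow-up".
- A wording that could be read as five (6.0, Follow-up Assessments): "There will be four additional follow up assessments for participants to complete", placed after the immediate post-test, although only three time points are then listed.
- Sample size 270 in sections 2.0 and 12.0, but 180 in section 1.0 and 60 per site (3 × 60 = 180) in section 25.0.

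**The concern.** A detectable odds ratio quoted over ranges of uptake and ρ should hold at the least favourable combination, here uptake .05 with ρ = .7. Binary outcomes carry little information at 5% prevalence, and a high within-person correlation means that repeat visits add little. An upper figure of only 2.3 at that corner with 135 per arm looks too optimistic.

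PrEP uptake and adherence form part of the primary hypothesis. Those already taking Truvada as PrEP are excluded (protocol 10.0), so the low-uptake scenario is a relevant one. If the stated power is wrong there, a true OR of 2.3 would be missed about a third to a half of the time, rather than the one time in five that the SAP implies.

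**Working it through.** **Inputs from the documents.** Power .80; uptake p₁ = .05 to .20; ρ = .4 to .7; compound symmetry (stated for STIs and carried over to PrEP); N = 270; m = 4 post-baseline assessments.

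**Inputs assumed.** 1:1 allocation (135 per arm), two-sided 5%, time-averaged difference, PrEP status available at all m assessments, no attrition. Equal allocation and no attrition favour the SAP.

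**Formulas.**
- Comparison-arm proportion: p₂ = p₁·OR / (1 − p₁ + p₁·OR).
- Variance factor: f = [1 + (m − 1)ρ] / m, which falls towards ρ as m grows without limit.
- Effective n per arm: 135 / f.
- Power: Φ{ (p₂ − p₁ − z·s₀) / s₁ }, where s₀² = 2p̄(1 − p̄)/n_eff, s₁² = [p₁(1 − p₁) + p₂(1 − p₂)]/n_eff, p̄ = (p₁ + p₂)/2 and z = 1.96.

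**Attempt to reproduce the stated range (m = 4, two-sided).** Detectable OR at 80% power:

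| Uptake | ρ = .4 | ρ = .7 |
|---|---|---|
| .05 | 2.60 | 3.02 |
| .10 | 2.09 | 2.36 |
| .20 | 1.80 | 1.99 |

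The full range is about 1.8 to 3.0, against 1.9 to 2.3 stated. The rows for .10 and .20 alone give 1.8 to 2.4, close to the SAP's figure. The row for .05 does not fit. A log-odds Wald version of that row gives 2.68 and 3.15.

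**Power at uptake .05 and OR 2.3, step by step.** p₂ = .115/1.065 = .108 and p̄ = .079.
- ρ = .4: f = (1 + 3 × .4)/4 = .55; n_eff = 135/.55 = 245; s₀ = .02435, s₁ = .02421; (.0580 − 1.96 × .02435)/.02421 = 0.42; power 66%.
- ρ = .7: f = (1 + 3 × .7)/4 = .775; n_eff = 135/.775 = 174; s₀ = .02890, s₁ = .02873; (.0580 − 1.96 × .02890)/.02873 = 0.05; power 52%.

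**Required size.** With independent single observations, OR 2.3 at uptake .05 needs 339 per arm. Multiplying by f gives 339 × .55 ≈ 187 (ρ = .4) and 339 × .775 ≈ 263 (ρ = .7), against 135 available.

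**Can the unstated inputs rescue the figure?** Uptake .05, 135 per arm:

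| Setting | OR, ρ = .4 | OR, ρ = .7 |
|---|---|---|
| Two-sided, m = 5 | 2.54 | 2.99 |
| Two-sided, m = 6 | 2.50 | 2.97 |
| Two-sided, m unlimited | 2.30 | 2.88 |
| One-sided 5%, m = 4 | 2.37 | 2.72 |
| One-sided 5%, m = 5 | 2.32 | 2.69 |
| One-sided 5%, m = 6 | 2.29 | 2.68 |
| One-sided 5%, m unlimited | 2.12 | 2.60 |

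At ρ = .7 nothing reaches 2.3. At ρ = .4, two-sided, limiting power at OR 2.3 is .799 (pooled variance) or .802 (unpooled, first reaching .80 at m = 294). One-sided, it is .79 at m = 5 and .80 at m = 6. At ρ = .5, two-sided, the limit is .71. OR 1.9 at uptake .05 never exceeds 55% power two-sided or 67% one-sided.

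**N = 270 read as per arm.** With m = 4, uptake .05 and ρ = .7 gives 2.28, but uptake .20 then gives 1.5 to 1.6, so this does not return the stated range either.

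**N = 180 (90 per arm, m = 4, two-sided).** Uptake .05: 3.1 to 3.7. Uptake .20: 2.0 to 2.3.

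**The case against.** The best defence is that the calculation is under-specified, so failure to reproduce it is not proof of error. Alpha and sidedness are not given. With one-sided 5% and five or six measures, uptake .05 paired with ρ = .4 gives about 2.3, and uptake .20 paired with ρ = .7 gives about 1.8 to 1.9. If low uptake was paired only with low ρ, the stated range is roughly recovered. That reading needs a one-sided test that the SAP does not mention and a pairing that it does not describe: it lets both inputs vary and does not link them.

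The floor on the variance factor also applies only to a time-averaged difference. The planned model has an intercept and a slope, and a slope contrast has no such floor. This stands as a reason to state the contrast. However, the sentence gives an odds ratio against a reference uptake rate, which describes a difference in level, and no rate of change is given from which a slope calculation could be made.

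A reader might infer that no number of repeated measures could ever deliver the stated power at 5% uptake. That goes too far. It holds at ρ = .7 on either sidedness, and two-sided from ρ of about .5, but at ρ = .4 OR 2.3 is borderline, as the working shows.

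A reader might also infer that this shows the trial to be underpowered for a primary outcome by these amounts. The documents do not support that directly. The sentence takes remote delivery as its reference, whereas the primary hypothesis and the randomisation set YMHP against standard of care.

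**Conclusion.** The concern holds in limited form. The range 1.9 to 2.3 does not cover the SAP's own inputs. At 5% uptake with the four scheduled assessments, the detectable OR is about 2.6 to 3.0, and power at OR 2.3 is 66% to 52%. Failure at the corner of uptake .05 and ρ = .7 does not depend on the number of measures or on sidedness. The figures at ρ = .4 do depend on them. At uptake of .10 or more the stated range is about right.

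The sizes rest on 1:1 allocation, two-sided 5%, a time-averaged contrast under compound symmetry and no attrition. Unequal allocation, attrition or an operative N of 180 would each make them worse. They carry over to the randomised comparison only if the same uptake range is taken for the standard-of-care arm.

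**What to change.** In the PrEP sentence of SAP 1.2.1, state alpha, sidedness, allocation, number of measures and the contrast tested, then re-run and report the detectable OR over every combination of uptake and ρ. Under the assumptions above that is about 1.8 to 3.0 at N = 270, or about 2.0 to 3.7 if N = 180 is the operative size; the two sample sizes must be reconciled first. The alternative is to keep an upper figure of about 2.3 to 2.4 and limit it to uptake of .10 or more.

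Either way, express the result for YMHP versus standard-of-care HIV testing, with the reference uptake taken as that of the standard-of-care arm.

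The cost is one rewritten sentence and a less favourable figure. No participants or visits are added.
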